#### **Adjustment of study drug dose level**

**Table 5-7 Safety and tolerability guidance for dose adjustments**

Parameter	Criteria
Potassium level	$K > 5.3\text{ mEq/L}$
Kidney function	

• eGFR reduction <math>\geq 35\%</math> compared to baseline; OR, serum creatinine of <math>\geq 0.5\text{mg/dl}</math> with at least a 25% decrease in eGFR

Blood pressure	

• No symptomatic hypotension or SBP <math>< 90\text{ mmHg}</math>

Adverse events (AEs) or conditions	

• No postural symptoms or any conditions that preclude continuation according to the investigator's judgment

Every attempt should be made to maintain subjects on target study drug Dose Level 3 for as long as possible throughout the study. If, however, in the opinion of the investigator, a patient is unable to tolerate the protocol-specified target dose, the investigator will manage the patient's treatment according to the below guidelines:

**Steps:****1. Adjust Concomitant Medications**

- Dose adjustments/elimination of concomitant medications may remedy the situation before reducing the dose of study treatment. If adjustment of the concomitant medications is not possible or does not alleviate the side effects of concern, THEN;

**2. Adjust Study Treatment Dose Level**

- Down-titrate study treatment to the previous dose level. The subject may continue receiving the lower dose level for a recommended period of 1 to a maximum of 4 weeks.
- A re-challenge to titrate back up to the target dose level should be attempted at 2 weeks, or when subject is deemed stable. THEN:

**3. Further Adjust Study Treatment Dose Level**

- If tolerability issues are not alleviated despite down-titration by one dose level, the investigator may down-titrate further to the next lower study treatment dose level. The subject may continue receiving the lower dose level for a recommended period of 1 to a maximum of 4 weeks. See Step 5.
- Again, once stable, the subject should be re-challenged with up-titration to the next higher dose level in an attempt to gradually bring the subject back to the target study treatment dose level (Dose Level 3).
- The investigator may choose the next dose level for down- or up-titration according to his or her clinical judgment.

**4. Stopping Study Treatment**

If needed, the study treatment may be stopped completely, however, every effort must be made to complete an end of study visit and obtain follow up health status information for any subject that withdraws from the study. See [Section 5.6.2](#)

**5. Study drug restart after temporary treatment interruption**

- Once the investigator considers the subject's condition appropriate for receiving the study drug, the investigator should re-start the subject on study treatment at the most appropriate and allowable dose level per his/her medical judgment.
- If tolerated, the subject should be titrated up to the next dose level every 1 to 4 weeks, as per the investigator's judgment.

- In some instances, Dose Level 1 or 2 could be maintained if the investigator considers that the subject's condition would not allow any further up-titration to the target dose of study medication (Dose Level 3). In this case, it would be acceptable to maintain the subject at Dose Level 1 or 2, whichever is the higher and tolerated dose level by the subject, but reasons for not getting to Dose Level 3 need to be captured in the eCRF.
- Should the subject not tolerate the re-start study drug dose level, he/she may be down-titrated again (if appropriate) or discontinued from study treatment.

Subjects re-started on the study drug will retain their original randomization and study identification numbers.

The IRT must be contacted to register any changes in the subject's study treatment dose level, including in cases of temporary and permanent withdrawal or re-start of the study drug, and to obtain the medication numbers of the study drug supplies required for the new study treatment dose level. All dose changes and interruptions must also be recorded on the Dosage Administration Record eCRF.

Study visits should occur as close as possible to the pre-defined visit and time schedule described in [Table 6-1](#). The timeframe between the regular visits should be maintained as scheduled, irrespective of the number of unscheduled visits that may be performed in between, or dose interruptions that may occur.

In case of pregnancy discovered during the study, the patient should be instructed to stop taking the study drug immediately. (See [Sections 6.5.6](#) and [Section 7.4](#))

### **5.5.6      Rescue medication for worsening heart failure**

At any time during the 8 week randomized, double-blind treatment epoch, investigators have the option to withdraw subjects from study treatment if they develop signs and symptoms of worsening heart failure for which the investigator would like to administer appropriate therapy.

- Appropriate adjustments, intensifications, or additions to concomitant medications should be considered before deciding to withdraw the subject from study treatment.
- **Subjects CANNOT receive ACE is and/or ARBs during the study. These medications can ONLY be administered if the investigator believes that the subject needs to be withdrawn from study treatment so that they may be treated with these therapies due to signs and symptoms of worsening heart failure.**
- **A 36 hour wash-out period is required if the investigator chooses to withdraw the subject from double-blind treatment and switch to sacubitril/valsartan or ACEi due to symptoms of worsening heart failure.**
- Use of rescue medication must be recorded on the appropriate Concomitant Medications eCRF.

Investigators will use clinical judgement to determine if subject's condition requires closer monitoring. Unscheduled visits are permitted as needed.

### **5.5.7 Concomitant medication**

The investigator must instruct the patient to notify the study site about any new medications he/she takes after the patient was enrolled into the study. All medications, procedures and significant non-drug therapies (including physical therapy and blood transfusions) administered after the patient was enrolled into the study must be recorded in the Concomitant Medications or Surgical and Medical Procedures eCRF as appropriate.

Each concomitant drug must be individually assessed against all exclusion criteria/prohibited medication. If in doubt the investigator should contact the Novartis medical monitor before randomizing a patient or allowing a new medication to be started.

#### **ACEi and ARBs:**

The concomitant use of open-label ACEI or ARB is strictly prohibited while the subject is receiving study medication. If the investigator believes that addition of an ACEI or ARB is necessary, then study drug must be discontinued. Study medication should be stopped 36 hours prior to addition of open-label ACEI.

#### **Other heart failure and cardiovascular medication**

If a subject's condition warrants any change in concomitant heart failure or cardiovascular medications, changes may be made at the investigator's discretion. Oral diuretics may be used and may be adjusted throughout the study duration at the discretion of the investigator.

#### **Medications and substances known to raise potassium levels**

Potassium sparing diuretics, potassium supplements, aldosterone antagonists, and any other medications known to raise potassium levels should be used with caution while the subject is receiving study medication due to the increased possibility of occurrence of hyperkalemia. Salt substitutes containing potassium chloride are also to be avoided when possible. Potassium levels should be monitored regularly especially in those who are receiving these medications.

Concomitant administration of renin inhibitors, such as aliskiren, is prohibited in patients with diabetes mellitus.

#### **Phosphodiesterase-5 (PDE-5) inhibitors**

PDE-5 inhibitors should be used with caution while the subject is receiving study medication due to the increased possibility of occurrence of hypotension.

#### **Nesiritide and intravenous nitrates**

The concomitant admission of sacubitril/valsartan with nesiritide or intravenous nitrates has not been studied. Given biological interaction between sacubitril and BNP, concomitant use of nesiritide (recombinant BNP) is prohibited. Intravenous nitrates are also prohibited.

### **5.5.8 Prohibited medication**

Use of the treatments displayed in the table below and [Appendix 9](#) is NOT allowed after the baseline phase. Please note the list of prohibited medication is not exhaustive. If you have any questions, the medical monitor should be contacted.

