#### **3.1      Study design**

This study is a multicenter, randomized, double-blind, double dummy, parallel group, active-controlled 8-week study with open label extension using medical device-grade subject worn sensors to measure waking and sleeping physical activity in the ambulatory outpatient setting. The 18 week study duration will consist of a 2-week baseline observation phase (with subjects continuing their current heart failure drug therapy), followed by an 8 week blinded treatment phase during which subjects are randomized (1:1) to either initiation of sacubitril/valsartan treatment or enalapril comparator, and finally an 8 week open label extension phase during which all subjects are treated with sacubitril/valsartan. Each subject will undergo a 36 hour washout period [during which ACEi (Angiotensin converting enzyme inhibitor), or study drug will be withheld] before the start of the randomized, blinded treatment phase, and again before beginning the open label extension phase. The study will include 8 office visits and 5 tele-visits.

Subjects will wear a wrist-worn actigraphy device continuously for the 18 week duration of the study, from the time of enrollment (the start of the 2 week baseline phase) to the end of the open-label extension phase (end of treatment week 16). During this 18 week interval, the devices will be exchanged five times during five study visits, to guard against data loss and ensure adequate battery life. Data will be collected continuously during the trial and although only data collected during assessment periods will contribute to prospectively defined endpoints, other data may be assessed in future analysis of patterns observed during the study. Additionally, continuous wear reduces opportunities for lapses in compliance while adding very minimal assessment burden for subjects.

Each assessment period is seven contiguous days. This will allow for continuous actigraphy recording over the seven day period.

**Figure 3-1** Study design

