### 3.2 Rationale for study design

The design of the study facilitates the assessment of change in sequential daily physical activity, [REDACTED] HF symptoms and health-related quality of life; between baseline to select time point assessment periods after randomized, blinded assignment to treatment with sacubitril/valsartan versus the active comparator enalapril. Assessment of the primary endpoint at 8 weeks captures the early impact of initiation of sacubitril/valsartan versus enalapril, which is the focus of the study.

Waking activity will be the primary endpoint, and sleep activity (a measure of sleep disturbance) is the secondary endpoint. Actigraphy, which has been well characterized for the measurement of both daytime and sleep physical activity variables, will be used to inform the primary and secondary endpoints.

[figure not shown]
Prior to randomization, there will be a 2 week phase where device familiarization and baseline assessment will be completed. The initial baseline week will provide an opportunity for the subjects to become familiar and acclimated to the testing devices and assessment routines, prior to entering the baseline phase of the study. Data from the second week of this phase, the 'baseline phase' (Week -1) will be considered as the baseline value for comparison to subsequent periods. Data collected outside of the defined measurement periods will be excluded from analysis for the defined study endpoints.

The 36-hour wash-out interval after randomization and before entering the open-label extension is required per the FDA approved USPI label because there is a potential for increased risk for angioedema in subjects who receive both an ACE inhibitor and the combination of sacubitril/valsartan.

The randomized comparison phase of 8 weeks provides the direct assessment of the initial and early changes associated with sacubitril/valsartan treatment to treatment with the active comparator enalapril.

The open label phase of 8 weeks provides the opportunity for every subject to receive sacubitril /valsartan. This results in one group of subjects that will receive sacubitril/valsartan for a total of 16 weeks, providing information on the endpoints after this duration of continuous therapy. It also provides the opportunity to evaluate changes after initiating sacubitril/valsartan in a group of subjects who all had been previously receiving enalapril treatment for 8 weeks.

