#### **4.2 Exclusion criteria**

Subjects fulfilling any of the following criteria are not eligible for inclusion in this study. No additional exclusions may be applied by the investigator, in order to ensure that the study population will be representative of all eligible subjects.

1. Subjects with a history of hypersensitivity to any of the study drugs, including history of hypersensitivity to drugs of similar chemical classes, or allergy to ACEIs, ARBs, or NEP inhibitors as well as known or suspected contraindications to the study drugs.
2. Subjects with a history of angioedema drug related or otherwise
3. Subjects with symptomatic hypotension or systolic blood pressure  $<$ 100 mmHg at screening or  $<$ 95 mmHg at randomization.
4. Subjects with any conditions in skin or upper extremities which would limit the ability to tolerate a wrist-worn actigraphy device on the nondominant arm for 24 hours/day for the duration of the study.
5. Subjects unwilling or unable to wear and operate the study measurement devices for the phases required.
6. Subjects who are currently hospitalized, or were discharged from the hospital within 4 weeks prior to enrollment.
7. Subjects who are already taking sacubitril/valsartan
8. Subjects who are nonambulatory or use mobility assistive devices such as motorized devices, wheelchairs, or walkers. The use of canes for stability while ambulating is acceptable.
9. Subjects with physical activity impairment primarily due to conditions other than heart failure such as:
  - Exertional angina
  - inflammatory or degenerative joint disease
  - gout
  - peripheral vascular disease

- neurologic diseases affecting activity or mobility

10. Subjects with nontypical circadian behavioral patterns (for example: shift workers actively rotating shifts, subjects with non-24-hour sleep wake disorder as result of blindness)

11. Subjects with tremor, rigor or mobility limitations affecting the nondominant arm (e.g. due to Parkinson's disease, joint contractures, paralysis, injury etc.)

12. Subjects with chronic obstructive pulmonary disease (COPD) who require supplemental oxygen.

13. Subjects using a continuous positive airway pressure (CPAP) devices or similar technology for treatment of sleep disorders

14. Subjects unwilling or unable to refrain from the use of prescription and/or over the counter (OTC) sleep aids for the duration of the study

15. Subjects with body mass index (BMI) > 35

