### **5.1.2 Additional treatment**

The protocol requires subjects to continue their current heart failure drug therapy, during the 2-week baseline phase.

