**Table 5-8      Prohibited medication (Please also see Appendix 9)**

Medication	Prohibition period	Action taken
ACEIs Inhibitors: benazepril, enalapril, Lisinopril, captopril, Ramipril, Fosinopril, Moexipril Quinapril, Trandolapril	Duration of study	Discontinue study treatment
Aliskiren (only subjects with concurrent diabetes)	Duration of study	Discontinue study treatment
Bile acid sequestering agents (such as cholestyramine or colestipol)	Duration of study	Switch to alternate agent to avoid interference with study drug absorption. If use of alternate agent is not appropriate, do not randomize or discontinue study drug treatment.
Nesiritide and intravenous nitrates	Duration of study	Do not randomize. If hospitalized, either interrupt or discontinue study treatment. Nesiritide and intravenous nitrates have not been studied. Oral, topical and sublingual nitrates are permissible.
Prescription and non-prescription medications taken for insomnia or to induce sleep (See Appendix 9 for details and examples)	Duration of study	Discontinue study treatment

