2.7.1 Secondary endpoints

The secondary endpoints include the following:

- Change in mean activity during sleep between baseline phase (mean of data collected during Week -1) and the final randomized treatment phase measurement (mean of data

collected during Week 8), as measured by actigraphy (activity counts per minute during daily sleep period, wrist-worn accelerometer).

- Change in mean activity during sleep between baseline phase (mean of data collected during Week -1) and each randomized treatment and open-label extension phase measurement, as measured by actigraphy (Weeks 1, 9, and 16) (activity counts per minute during daily sleep period, wrist-worn accelerometer).
- Change in mean activity counts during the most active 30 minutes of the patient's day between baseline phase (mean of data collected each day during Week -1) and each randomized treatment and open-label extension phase measurement (Weeks 1, 9, and 16), as measured by wrist worn accelerometer collected actigraphy.

Endpoints will be based on the mean of data collected for at least 5 out of the 7 days during the given week.

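### Protocol 5.5.8 and exclusion 14 start the sleep-aid prohibition at different times, and the disputed period contains Week -1, the baseline for the sleep endpoints

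*Protocol*

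**What the plan says.** Four parts of the protocol bear on when sleep aids are prohibited.

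- Section 5.5.8, which governs Table 5-8 and Appendix 9 together: "Use of the treatments displayed in the table below and [Appendix 9](#) is NOT allowed after the baseline phase".
- Exclusion criterion 14 (Section 4.2) excludes "Subjects unwilling or unable to refrain from the use of prescription and/or over the counter (OTC) sleep aids for the duration of the study".
- Table 5-8 has a row for "Prescription and non-prescription medications taken for insomnia or to induce sleep". Its prohibition period is the whole study, and its only listed action is to stop study treatment.
- Section 3.1 fixes what the whole study means: "The 18 week study duration will consist of a 2-week baseline observation phase", followed by the blinded and open-label phases.

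The sleep endpoints are measured from inside the baseline period. Protocol Section 3.2 states: "Data from the second week of this phase, the 'baseline phase' (Week -1) will be considered as the baseline value". SAP 2.7.1 defines the Week 8 sleep endpoint as "Change in mean activity during sleep between baseline phase (mean of data collected during Week -1) and the final randomized treatment phase measurement". If Week -1 is missing or unevaluable, SAP 2.5.3 (applied to the secondary endpoints by SAP 2.7.3) falls back to the week before.

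Neither document states a sleep-aid washout before Week -1, or an analysis rule for baseline sleep data recorded while a patient was taking an Appendix 9 drug. SAP Section 5.6 lists no protocol deviation that removes a patient from an analysis set.

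**The concern.** Section 5.5.8 and exclusion 14 give different start points for the same prohibition, and the period between them holds the baseline measurement of every sleep endpoint that is taken from Week -1. A site that worked from 5.5.8 could treat sleep-aid use in Weeks -2 and -1 as outside the prohibition and enforce it only from randomization. Such a patient's change in sleep activity would mix the effect of stopping the sleep aid with any effect of study treatment.

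The sleep-aid row of Table 5-8 does not help in that period, because no study treatment has yet been given that could be stopped. Two other rows of the table, bile acid sequestrants and nesiritide/intravenous nitrates, do name a step before randomization.

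At stake are the precision of the randomized sleep comparisons and, more directly, the single-arm changes from Week -1 at Weeks 9 and 16.

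**Working it through.** **1. Compare the windows.**

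| Source | Prohibition on sleep aids starts | Covers Week -1? |
|---|---|---|
| Protocol 5.5.8 | after the baseline phase | no |
| Exclusion 14, with Section 3.1 | start of the 18 weeks | yes |
| Table 5-8, sleep-aid row | whole study, read literally | yes, but see below |

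Table 5-8 is the weaker witness. Its whole-study label also stands on the ACE inhibitor row, yet Section 5.1.2 says: "The protocol requires subjects to continue their current heart failure drug therapy, during the 2-week baseline phase". For a patient on an ACE inhibitor the label cannot literally include baseline, so it may not do so for sleep aids either. The firm conflict is between 5.5.8 and exclusion 14.

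**2. Reproduce the plan's power for sleep activity at Week 8.** Inputs from Protocol 9.8 and SAP Section 3: 136 randomized 1:1, difference 3.5 counts/min, SD 4.9, two-sided alpha 0.05, 20% drop-out, 10% non-evaluable.

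- Evaluable: 136 × (1 − 0.20 − 0.10) = 95.2, or 47.6 per arm.
- Standard error of the difference: 4.9 × √(2/47.6) = 1.00.
- Power from the noncentral t: 93.2%. The stated 93% reproduces.

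**3. Effect on the randomized comparison.** The documents give neither the share of patients who might use a sleep aid in Week -1 nor the effect of stopping one, so both are assumptions. Let a share q use one in Week -1 and not later, and let stopping shift their change by d counts/min. The mean shift in each arm is q × d, and the SD of the change becomes √(4.9² + q(1 − q)d²). Power is for 3.5 counts/min with 47.6 per arm.

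| d | q | Mean shift | SD | Power |
|---|---|---|---|---|
| none | – | 0 | 4.90 | 93.2% |
| 1 | 5% / 10% / 20% | 0.05 / 0.10 / 0.20 | 4.91 / 4.91 / 4.92 | 93.1% / 93.1% / 93.0% |
| 3.5 | 5% / 10% / 20% | 0.18 / 0.35 / 0.70 | 4.96 / 5.01 / 5.10 | 92.6% / 92.1% / 91.2% |
| 7 | 5% / 10% / 20% | 0.35 / 0.70 / 1.40 | 5.13 / 5.33 / 5.64 | 90.9% / 88.7% / 85.0% |

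Use in Week -1 precedes randomization, so the mean shift is the same in expectation in both arms and cancels in the difference. What remains is chance imbalance, with SD d × √(2q(1 − q)/48). For d = 3.5 this is 0.16, 0.21 and 0.29 at q = 5%, 10% and 20%. Even the largest adds little to the standard error: √(1.00² + 0.29²) = 1.04, about 4% wider.

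This treats the endpoint as a change score, as the plan's own sample size does. The planned ANCOVA also adjusts for baseline, which the table does not model.

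**4. Effect on the single-arm tests.** At Weeks 9 and 16 the sacubitril/valsartan arm is tested by paired t-test from Week -1 (SAP 2.7.2). There is no control group, so q × d enters the estimate in full: 0.18, 0.35 or 0.70 counts/min for d = 3.5. If the SD of 4.9 and 47.6 patients also applied at those weeks (a further assumption), the standard error of the mean change would be 4.9/√47.6 = 0.71. The shift would then be about a quarter, a half or one standard error. The enalapril arm's repeat of these tests uses Week 8 as its baseline, so Week -1 does not enter there.

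**The case against.** The strongest reply is that other clauses already prevent the scenario. Exclusion 14 covers the baseline weeks. Protocol 5.3 allows randomization only after the investigator confirms every eligibility criterion. Section 5.5.7 requires each concomitant drug to be checked against the exclusion criteria and the prohibited list, with the medical monitor consulted before randomization if in doubt. A patient who took a hypnotic in Week -1 has visibly not refrained. On this view 5.5.8 was worded with ACE inhibitors in mind and is merely silent about sleep aids at baseline. Where exclusion 14 is followed from enrollment, Week -2 also gives some interval before the measured week.

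Most of this stands. It makes the problem conditional on a site reading 5.5.8 as the operative rule. It does not remove the contradiction, because 5.5.8 names Appendix 9 expressly and its start point differs from exclusion 14. A reader might infer that 5.5.8 authorizes sleep aids during baseline. It does not: it leaves that period outside its own prohibition, and exclusion 14 still applies.

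The reply is also right that the effect on the Week 8 comparison is small, and that the assumed prevalence and shift have no source in the documents. The upper end of the prevalence range is generous for patients who have had to pass exclusion 14.

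**Conclusion.** The point holds as an inconsistency that should be reconciled. Its consequences are limited and depend on a site following 5.5.8 in place of exclusion 14.

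- **Randomized Week 1 and Week 8 sleep comparisons:** no bias on average. The calculation, done for Week 8, shows a small loss of precision: power of about 91% to 93% against 93.2% if 5% to 20% of patients shift by an assumed 3.5 counts/min. It reaches 85.0% only when both the share (20%) and the shift (7 counts/min) are set high.
- **Week 9 and 16 paired tests in the sacubitril/valsartan arm:** the shift enters directly, and nothing in the planned analysis would reveal it.

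Three stronger readings go beyond the documents. A reader might infer that the secondary objective can no longer be answered. That objective is a comparison of two randomized arms, and use before randomization is balanced in expectation. A reader might take 3.5 counts/min as a known sleep-aid effect, because the sleep design figures cite a study whose title concerns zolpidem. The documents report no such effect, and 3.5 is used here only as a yardstick. A reader might also extend the point to the primary waking-activity endpoint, but the documents say nothing about how a bedtime sedative would alter it.

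Which prohibition window is clinically right is not judged here.

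**What to change.** **Protocol.** Reconcile 5.5.8, exclusion 14 and Table 5-8 so that all three state one prohibition window for sleep aids, separate from the one for ACE inhibitors if that is what was meant. State what happens when sleep-aid use is found before randomization, since the action now listed cannot apply then.

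**SAP.** Add a sensitivity analysis of the sleep endpoints that excludes patients with an Appendix 9 drug recorded as taken during the week used as their baseline: Week -1, or Week -2 under the fallback. Two details matter.

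- Use recorded dates, not imputed ones. Under SAP 5.1.3, a start date with the day missing in the month of first treatment is set to the first treatment date, so use that began in Week -1 could appear to begin on Day 1. Report how many patients cannot be classified from recorded dates.
- Do not drop individual nights after randomization. Sleep-aid use then may itself respond to treatment, and removing those nights could bias a comparison that the inconsistency leaves unbiased. Exclusion based on the baseline week rests on information from before randomization and does not have this problem.

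**Cost.** The change needs a short protocol clarification and one added sensitivity analysis. Concomitant medications are already recorded from Visit 1, so no new data are needed. The sample in the sensitivity analysis would be slightly smaller, and the planned 136 patients and stated 93% power are unaffected.
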